- b) Subjects with any bacterial infection within the last 60 days prior to screening (enrollment), unless treated and resolved with antibiotics, or any chronic or history of recurrent bacterial infection (such as chronic pyelonephritis, osteomyelitis and bronchiectasis)
- c) Subjects who have a history of systemic fungal infections (such as histoplasmosis, blastomycosis, or coccidioidomycosis)
- d) Subjects with history of recurrent herpes zoster (more than 1 episode) or disseminated (more than 1 dermatome) herpes zoster or disseminated herpes simplex, or ophthalmic zoster will be excluded. Symptoms of herpes zoster or herpes simplex must have resolved more than 60 days prior to screening visit (enrollment)
- e) Subjects with evidence (as assessed by the investigator) of active or latent bacterial or viral infection at the time of potential enrollment, including subjects with history or evidence of Human Immunodeficiency Virus (HIV) infection or who have a positive HIV test at screening
- f) Any significant concurrent medical condition at the time of screening or baseline visit, including, but not limited to, the following:
 - i) Any major illness/condition or evidence of an unstable clinical condition (eg, renal, hepatic, hematologic, gastrointestinal, endocrine, pulmonary or active infection/infectious illness) that, in the Investigator's judgment will substantially increase the risk to the subject if he or she participates in the study
 - ii) Cancer or lymphoproliferative disease within the previous 5 years (other than resected cutaneous basal cell or squamous cell carcinoma that has been treated with no evidence of recurrence). Subjects with a history of lymphoma at any time are excluded
 - iii) Female subjects with a breast cancer screening suspicious for malignancy, and in whom the possibility of malignancy cannot be reasonably excluded following additional clinical, laboratory or other diagnostic evaluations
 - iv) Class III or IV congestive heart failure as defined by the New York Heart Association
 - v) Acute coronary syndrome (eg, myocardial infarction, unstable angina pectoris) and/or any history of significant cerebrovascular disease within 24 weeks before screening
 - vi) Liver cirrhosis or other underlying liver disease (eg, non-alcoholic steatohepatitis, primary sclerosing cholangitis, primary biliary cirrhosis/cholangitis)
 - vii) Any significant coagulation or platelet function disorders (eg, von Willebrand's disease)

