 - viii) Any gastrointestinal condition that could impact study drug absorption
 - ix) Any other concomitant medical conditions that, in the opinion of the investigator, might place the subject at unacceptable risk for participation in this study

- g) Major surgical intervention or scheduled surgery during the 8 weeks preceding enrollment
- h) Subjects currently on hydroxychloroquine who cannot provide documentation of an ophthalmologic evaluation (including evaluation of the retina) or who have evidence of retinopathy within 6 months of screening
- i) Donation of blood to a blood bank or in a clinical study (except a screening visit) within 4 weeks of study drug administration (within 2 weeks for plasma only)
- j) Blood transfusion within 4 weeks of study drug administration
- k) Inability to be venipunctured and/or tolerate venous access
- l) Subjects with a history of (within 12 months of signing the consent), or known current problems with drug or alcohol abuse
- m) Subjects with a history or suspicion of unreliability, poor cooperation, or non-compliance with medical treatment
- n) Subjects who have received treatment with an investigational drug within 12 weeks or less than 5 terminal half-lives of elimination (whichever is longer) of randomization (Day 1)
- o) Live vaccine administration to subjects within 30 days of enrollment, during the screening or study periods, or for 8 weeks after completion of dosing
- p) Subjects who are unwilling or have difficulty swallowing oral tablets

3. Physical and Laboratory Test Findings

- a) Subjects with positive HBsAg, or subjects with positive anti-HBc antibody with detectable quantitative HBV DNA. Subjects with negative HBsAg but with high risk for latent HBV infection (including subjects with known family history of HBV infection, HBV carrier, personal medical history of hepatitis or blood transfusion history) should be tested for quantitative HBV DNA at the investigator's discretion. Subjects with positive quantitative HBV DNA are excluded from the study
- b) Hepatitis C antibody-positive subjects who are also HCV positive by confirmatory testing such as PCR
- c) Positive HIV test
- d) Have any clinically significant laboratory abnormalities (confirmed by repeat testing) including but not limited to:
 - i) Hepatic
 - (1) ALT $\geq 2 \times$ ULN (Upper limit of normal)
 - (2) AST $\geq 2 \times$ ULN
 - (3) Total bilirubin $\geq 1.5 \times$ ULN
 - ii) Hematology

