5 STUDY ASSESSMENTS AND PROCEDURES

5.1 Flow Chart/Time and Events Schedule

Table 5.1-1: Screening Procedural Outline (IM128035)^a

Procedure	Screening Visit 1	Screening Visit 2 ^b	Notes
Eligibility Assessments			
Informed Consent	X		
Inclusion/Exclusion Criteria	X	X	
Medical History	X		
Enroll subjects (contact Central Randomization System)	X		Contact IVRS/IWRS for subject number after signing consent. If subject does not meet eligibility criteria, contact IVRS/IWRS to screen fail subject.
Concomitant Medication review	X	X	See Section 3.4 Hydroxychloroquine (if used) must be at a stable dose for 8 weeks prior to screening. Corticosteroids (if used) must be ≤ 10 mg/day for at least 14 days prior to dosing; no changes to other medications within 14 days of dosing.
ESSDAI	X		See Section 5.4.1
Unstimulated salivary flow	X		See Section 5.4.2.2
Anti-SSA/Ro and anti-SSB/La autoantibody	X		
Safety Assessments			
Physical Examination	X		
Targeted Physical Examination		X	targeted PE for steroid taper visits only (not HCQ)
Vital Signs	X	X	
Height and weight	X		
ECG	X		
Chest X-Ray	X		Required only if not performed within 6 months of signing informed consent and/or if documentation of previous CXR is not on file. See Section 5.3.3 .

Table 5.1-1: Screening Procedural Outline (IM128035)^a

Procedure	Screening Visit 1	Screening Visit 2 ^b	Notes
Safety Laboratory Tests	X		At least 10 hour fast required prior to collection of sample. Must include complete blood count with differential, chemistries, liver function tests, PT/PTT, amylase/lipase and urinalysis.
TBNK profile	X		For subjects who have been treated with rituximab in the past. Must be reviewed for CD19+ B cell count > 10/ μ l prior to dosing on Day 1.
TB Screening	X		See Section 5.3.3
HBsAg, HBcAb	X		May also include reflex HBV DNA testing where required locally
HCV antibody	X		If positive, reflex to HCV confirmation test such as PCR
HIV test	X		Performed locally or centrally per local regulations
Pregnancy Test (WOCBP only) or FSH (to confirm menopause)	X		Serum pregnancy test to be performed only if urine test is positive or un-interpretable, or if necessary as per local/institutional requirements.
Hydroxychloroquine PK sampling (subjects on HCQ only)		X	Subjects should bring their HCQ dose to the clinic for screening Visit 2 to be taken in the clinic. Serial PK sampling at 0hr, 2hr, 4hr after HCQ dosing.

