Protein Glucose Blood Leukocyte esterase Specific gravity pH Reflex to microscopic examination of the sediment if blood, protein or leukocytes esterase are positive on the dipstick Spot urine protein/creatinine ratio [UPCR] (screening only, in subjects with clinical suspicion of nephrotic syndrome or clinically significant protein on urinalysis)
Serology
Serum for hepatitis C antibody, hepatitis B surface antigen, hepatitis B core antibody (screening only) HIV testing (screening only, may be performed locally or via central lab per local requirements) Auto-immune serology: ANA, Anti-SSA/Ro, Anti-SSB/La, Rheumatoid Factor Immunoglobulin levels: IgM, IgA, and IgG Complement levels (C3, C4, CH50)
Other Analyses
IGRA/TB Test
Pregnancy test (WOCBP only; urine test, serum test only to be performed if urine test is positive or uninterpretable, or if necessary as per local/institutional requirements).
Follicle stimulating hormone (FSH): (screening only, for post-menopausal women only, see Section 3.3.3)

Results of all laboratory tests required by this protocol must be provided to BMS, either recorded on the laboratory pages of the CRF or by another mechanism as agreed upon between the investigator and BMS (eg, provided electronically). If the units of a test result differ from those printed on the CRF, the recorded laboratory values must specify the correct units. Any abnormal laboratory test result considered clinically significant by the investigator must be recorded on the appropriate AE page of the CRF (see [Section 6.1.1](#)).

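### Exclusion 3(a) cannot be assessed for an HBsAg-negative, anti-HBc-positive subject without an HBV DNA result, but the screening schedule makes that test optional

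*Protocol*

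**What the plan says.** **The criterion.** Exclusion 3(a) in Protocol Section 3.3.2 has three parts.

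- It first excludes "Subjects with positive HBsAg, or subjects with positive anti-HBc antibody with detectable quantitative HBV DNA".
- It then turns to HBsAg-negative subjects thought to be at high risk of latent infection, giving family history, carrier status, past hepatitis and transfusion as examples. These subjects "should be tested for quantitative HBV DNA at the investigator's discretion".
- It closes with "Subjects with positive quantitative HBV DNA are excluded from the study".

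**The schedule.** Table 5.1-1 (Section 5.1) requires HBsAg and HBcAb of everyone at Screening Visit 1. The only mention of HBV DNA is the note on that row: "May also include reflex HBV DNA testing where required locally". The next row, for HCV antibody, carries the note "If positive, reflex to HCV confirmation test such as PCR".

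**The laboratory list.** The serology part of Section 5.3.2 names hepatitis B surface antigen and core antibody at screening. It does not name HBV DNA.

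**The concern.** An eligibility rule works only if the schedule produces the result that the rule reads. For one serological pattern, 3(a) reads a quantitative HBV DNA result, while the schedule leaves it to local requirements whether that result exists. Sites work from the schedule, so one exclusion could be applied differently from site to site, and at some sites not at all.

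Two things are at stake.

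- **Subject protection.** The sponsor has itself judged detectable HBV DNA to be disqualifying, and two of the three arms receive a CD28 antagonist or a BTK inhibitor.
- **Interpretation of liver findings.** SAP Section 7.6.1.1 lists increased transaminases among the events of special interest. Protocol Section 6.6 defines potential drug-induced liver injury partly by the absence of another apparent cause, with viral hepatitis named as one such cause. Section 3.5 makes potential liver injury a reason to stop study drug. If HBV DNA was never measured at entry, such an event is harder to classify.

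**Working it through.** No arithmetic applies. The check sets the criterion beside the schedule for each possible serological result, and then asks whether any other provision fills the gap.

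**Step 1. What 3(a) needs and what Table 5.1-1 delivers**

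| Screening serology | What 3(a) needs in order to decide | What the schedule secures |
|---|---|---|
| HBsAg-positive | Nothing further; excluded | Sufficient |
| HBsAg-negative, anti-HBc-positive | HBV DNA, detectable or not | Only a test that may be done where locally required |
| HBsAg-negative, anti-HBc-negative | HBV DNA only if the investigator tests a high-risk subject | Consistent with a permissive note |

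The permissive note suits the third row. It does not suit the second, where eligibility depends on the DNA result alone.

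**Step 2. Whether 3(a) itself orders the test in the second row.** It does not. Its only testing instruction concerns high-risk HBsAg-negative subjects and leaves the decision to the investigator. Anti-HBc positivity is not among the risk examples. If it is nevertheless read as marking high risk, the test becomes discretionary. On neither reading is it required.

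**Step 3. How the protocol handles comparable tests.** Exclusion 3(b) for hepatitis C has the same two-step form, an antibody followed by a confirmatory test, and its row in Table 5.1-1 makes the second step automatic. The TBNK row, for subjects previously given rituximab, requires the B-cell count to be reviewed before Day 1 dosing. Of these three rows, only hepatitis B leaves the deciding result optional.

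**Step 4. Whether a backstop orders the test**

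- Sections 3.3 and 3.3.2 insist that all criteria be met. That states the aim but generates no result.
- Section 5.3 requires assessment results to be reviewed on Day 1 before randomisation. It covers the assessments that were done and does not add one.
- Section 5.1.1 permits repeats of scheduled screening tests but requires none.
- Exclusion 2(e) covers "Subjects with evidence (as assessed by the investigator) of active or latent bacterial or viral infection at the time of potential enrollment". It rests on evidence, and an untested subject may show none.

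Each of these lowers the chance of a wrong entry. None of them orders an HBV DNA test.

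**Step 5. Size.** The expected number of subjects randomised with detectable HBV DNA would be N × (proportion HBsAg-negative and anti-HBc-positive) × (proportion of those left untested) × (proportion of those with detectable DNA). The documents give N, which is 75 with a maximum of 120. They give none of the other three factors, so no count is offered.

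**The case against.** The strongest reply is that the schedule does not override the criteria. An investigator holding a positive anti-HBc result cannot honestly confirm 3(a) on Day 1 without a DNA result, so a subject slips through only if the site also misapplies 3(a). Moreover, 3(a) itself uses the language of discretion, so the note could be read as agreeing with it. The laboratory manual and the central laboratory's instructions, mentioned in Sections 5.2 and 5.3.2, may already set up a reflex test, and they are not available for review.

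Much of this stands, and it limits the point to what can happen. It does not remove the mismatch. The discretion clause is written for high-risk subjects, whereas the anti-HBc clause is unqualified. An investigator reading the table note would also have grounds to think the test unnecessary where no local rule asks for it.

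A reader might also infer several stronger things that the documents do not support.

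- **That every anti-HBc-positive subject needs a DNA result.** HBsAg-positive subjects are excluded without one.
- **That the absence of HBV DNA from the Section 5.3.2 list shows it will not be done.** The HCV confirmatory test is missing from that list too, although Table 5.1-1 clearly requires it.
- **That the exclusion never operates where there is no local requirement, or that a missed case cannot surface later.** The Day 1 eligibility check remains. Liver tests are repeated on Day 1, at Weeks 1, 2, 4, 6, 8, 10 and 12, and at Week 18. Raised transaminases and underlying liver disease are separate exclusions, and a data monitoring committee reviews safety. These are partial safeguards and do not replace the entry test.
- **That an assumed anti-HBc prevalence gives the number at risk.** It would count subjects whose eligibility is undetermined, not those with detectable DNA, and it would ignore sites that do test.

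**Conclusion.** The point holds for HBsAg-negative, anti-HBc-positive subjects. Their eligibility under 3(a) turns on an HBV DNA result that the screening schedule leaves optional and that no other visible provision orders. A site can follow the schedule exactly and still randomise such a subject with the exclusion unassessed.

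The conclusion rests on the protocol text alone. It assumes that at least some sites have no local requirement for the test and that no document outside the protocol already imposes one. It says that such entry is possible, not that it will happen. The number affected cannot be estimated. Nothing in the primary endpoint, the analysis model or the sample size depends on it. The consequences are for subject protection, uniform application of the criterion across sites, and interpretation of liver events.

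**What to change.** Exclusion 3(a) and the HBsAg/HBcAb note in Table 5.1-1 must be reconciled so that the schedule obtains, before randomisation, the result that 3(a) uses to decide eligibility. The HCV row is a model for the form of wording. For consistency, the Section 5.3.2 serology list should be brought into line at the same time.

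Within 3(a), the sponsor should state which subjects the investigator-discretion sentence covers, and in particular whether it is meant to reach anti-HBc-positive subjects. The text refers only to HBsAg-negative subjects at high risk and does not give their anti-HBc status.

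The exclusion threshold does not change. The cost is the table and criterion wording, a reflex set-up at the laboratory, a few assays on the screening sample and possibly a few more screen failures. If the laboratory instructions already provide the reflex test, only the protocol wording needs to change.

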4.5 Selection and Timing of Dose for Each Subject

All drug dosing should occur after all study-related assessments, including blood draws, are completed. Refer to [Section 5.3](#) for additional information on the order of procedures.

After randomization, study drug will be dispensed according to the assignment by the IVRS/IWRS system. Study drugs are blinded and will be supplied in bottles for BMS-986142 and its matching placebo for home administration. Doses of lulizumab or matching placebo are to be administered subcutaneously in the clinic or by a health care professional (eg, visiting nurse) in the home if approved by local IRB/EC and the investigator. Doses of BMS-986142 at 350 mg or matching placebo are to be administered orally q24h (one time/day) with water and may be taken with or without food. Three tablets, one tablet from Bottle A and two tablets from Bottle B, will be taken all at the same time, once/day every day. Subjects should be instructed to bring their oral study drug (BMS-986142 or placebo) to be taken at the investigational site at every scheduled visit (eg, weekly if home visits are not performed) to avoid confusion about the timing of dose administration, given the frequency of PK assessments and study procedures during the study. On Day 1 and at Weeks 2, 4, 6, 8, and 10, study drug will be administered in the morning at the study site and after blood samples have been collected and questionnaires have been completed. For subjects who are on a stable dose of HCQ, subjects must also bring their HCQ dose to the site on Day 1, Day 8, Week 2 (Day 15), Week 4 (Day 29) and Week 12 (Day 85) of the study as well as the two follow up visits at Week 15 (Day 106) and Week 18

(Day 127), as the HCQ dose will be administered at the same time as the study drugs in the morning at the study site to enable pre-dose PK samples to be taken. Two post-dose PK samples (2 and 4 hours after dosing) for HCQ and study drugs will also be collected at the Day 8 visit. However, at other visits, drug should be taken at approximately the same time each day.

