- d Biopsy procedure window of ± 5 days (5 days **prior to dosing only** for Day 1/baseline biopsy)
- e Ophthalmologic procedure window of ± 5 days (5 days **prior to dosing only** for Day 1/baseline assessments), all assessments must be performed at same visit

In the event multiple assessments are required at the same study visit, the assessments should be performed in the following order whenever possible:

- 1) Disease activity assessments (eg, ESSDAI, ESSPRI, symptom scales)
- 2) Vital signs, physical exams, ECGs
- 3) Salivary flow assessments
- 4) Blood draws for safety labs, pre-dose PK assessments and biomarker assessments
- 5) Administration of study medication(s) and HCQ (if applicable)
- 6) Post-dose PK assessments (if applicable)
- 7) Ophthalmologic assessments (if performed on the same visit day)
- 8) Optional lip or parotid salivary gland biopsy

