5.4 Efficacy Assessments

All assessments should be performed prior to dosing.

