5.4.2 Secondary Efficacy Assessments

5.4.2.1 Ophthalmologic Assessments

The following procedures should be performed at baseline/Day 1, Week 4, Week 8, and Week 12 by an ophthalmologist or optometrist experienced in the diagnosis and treatment of Sjögren's syndrome subjects and according to the methods described in Whitcher, et al.⁶⁵ A visit window of ± 5 days to perform the ophthalmologic assessments is acceptable (baseline/Day 1 assessment can be performed up to 5 days **prior to dosing** only), but all assessments must be performed during the same visit. The use of alternative ocular dyes may be permitted per local standards and/or regulations, and after consultation with the BMS Medical Monitor.

- Schirmer's test: The test (without anaesthesia) is performed by placing a narrow calibrated filter-paper strip in the inferior cul-de-sac of each eye. Aqueous tear production is measured by the length in millimeters that the strip wets during the 5 minute test period
- Tear break-up time (TBUT): Determined by instilling fluorescein dye and evaluating the stability of the pre-corneal tear film. After several blinks, the tear film is examined using a broad beam of the slit-lamp (biomicroscope) with a cobalt blue filter. The TBUT, defined as the time in seconds between the subjects's last blink and the first appearance of a random dry spot on the corneal surface, is measured 3 times and the mean value is recorded
- Ocular surface staining: The test is performed by instillation of fluorescein dye and either lissamine green or Rose bengal dye to stain the cornea and conjunctiva, respectively. After instilling the dye, the ocular surface is examined through a slit lamp (biomicroscope) the staining pattern is recorded per the method described in Whitcher, et al⁶⁵

The results from each of the above procedures will be recorded in site source records as well as entered into the corresponding eCRF provided by BMS or designee.

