8.2 Analysis Window for Longitudinal Assessments

8.2.1 Baseline Value

For each subject, the baseline value of a parameter is defined as the last assessment of that parameter on or prior to the date/time of the first dose of the double-blind study medication.

If time of measurement of a parameter or time of first dose are missing, then the baseline value is defined as the last assessment of that parameter on or prior to the date of the first dose of the double-blind study medication.

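### The recommended visit order puts Day 1 eye tests and biopsy after the first dose, contradicting the pre-dose baseline rule; a site that follows it leaves either no ocular baseline or a post-dose one

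*Protocol*

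**What the plan says.** Below Table 5.1-2 the Protocol gives a numbered sequence for visits with several assessments: "the assessments should be performed in the following order whenever possible". Disease activity scores, including ESSDAI, come first. Dosing is "5) Administration of study medication(s) and HCQ (if applicable", post-dose PK is step 6, the eye tests are "7) Ophthalmologic assessments (if performed on the same visit day", and the optional lip or parotid biopsy is step 8. No visit is excepted.

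Other parts of the Protocol put these procedures before dosing:

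- Section 4.5: "All drug dosing should occur after all study-related assessments, including blood draws, are completed".
- Section 5.4: "All assessments should be performed prior to dosing".
- Footnote e to Table 5.1-2, on the eye tests: "5 days prior to dosing only for Day 1/baseline assessments), all assessments must be performed at same visit". Footnote d sets the same limit for the baseline biopsy.
- Section 5.4.2.1: "A visit window of ± 5 days to perform the ophthalmologic assessments is acceptable (baseline/Day 1 assessment can be performed up to 5 days" before dosing, and not after it.

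SAP 8.2.1 defines baseline as "the last assessment of that parameter on or prior to the date/time of the first dose of the double-blind study medication". If the time of the measurement or of the first dose is missing, the rule falls back to the calendar date alone.

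**The concern.** Ocular surface staining, Schirmer's test and tear break-up time, each as change from baseline at Weeks 4, 8 and 12, are secondary endpoints. All depend on one Day 1 (or slightly earlier) examination. A site working through the list on Day 1 would give the first dose, wait for the post-dose PK sample, and only then examine the eyes. That examination is not a pre-treatment measurement, and the SAP does not treat it consistently. The same conduct leads either to exclusion of the subject or to a post-dose baseline, depending on whether two clock times were recorded. A baseline missed before the first dose cannot be recovered afterwards.

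**Working it through.** The plan states no figure for this point, so the check is mainly a comparison of texts.

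**1. Does the conflict reach Day 1?** Section 5.4.2.1 schedules eye tests at Day 1 and Weeks 4, 8 and 12 (Days 29, 57 and 85). Tables 5.5-1 and 5.5-2 show same-visit post-dose PK samples during treatment only on Days 1 and 8. By those tables, Day 1 is the only visit at which steps 6 and 7 both apply. (The text of Section 5.5 also mentions serial hydroxychloroquine sampling on Day 29, but Table 5.5-2 shows only a pre-dose sample that day.) Section 5.3 names the assessments that precede the first dose and does not name the eye tests. Its general pre-dose rule allows for exceptions indicated elsewhere, and a site could read the list as one.

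**2. Is there an earlier value to fall back on?** Table 5.1-1 schedules no eye test at Screening.

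**3. What happens to a subject without a baseline?** Under SAP 7.1.5.1 the response is change from baseline, with baseline also a covariate. SAP 8.3.1 imputes nothing. Such a subject cannot enter the three ocular models.

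**4. Outcomes for a subject examined on Day 1 with no earlier value**

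| Exam relative to first dose | Clock times | Result under SAP 8.2.1 |
|---|---|---|
| Before | Both recorded, or either missing | Valid pre-dose baseline |
| After | Both recorded | No baseline; lost from all three ocular endpoints |
| After | Either missing | Post-dose value used as baseline |

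**5. Illustrative size.** Let f be the fraction with no baseline, spread evenly over arms, with the outcome SD unchanged. The standard error of a two-arm difference is proportional to 1/√n, so it rises by the factor 1/√(1 − f). With the planned 75 subjects:

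| f (assumed) | Subjects lost, 75 × f | 1/√(1 − f) | Rise in SE |
|---|---|---|---|
| 0 | 0 | 1.000 | 0% |
| 10% | 7.5 | 1/√0.9 = 1.054 | about 5% |
| 30% | 22.5 | 1/√0.7 = 1.195 | about 20% |
| 50% | 37.5 | 1/√0.5 = 1.414 | about 41% |

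The documents give no value for f. It is the share examined after dosing with both times recorded, not the share examined on the same day.

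**The case against.** The pre-dose rule for baseline eye tests is explicit. It stands in footnote e, directly above the list, and again in Section 5.4.2.1, with Sections 4.5 and 5.4 behind it. The list is generic and applies only where possible. A site that examined the eyes after the first dose would break a specific rule in order to follow a soft default. The ocular endpoints are secondary, with nominal p-values and no multiplicity adjustment, and no mechanism is evident by which losses would differ between blinded arms.

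Most of this stands, and it limits the size of the point. It does not remove the conflict. Footnote e is written as a window in days, so a site can take the day from the footnote and the order within the day from the list. The qualifier asks sites to follow the list when they can, so a site that complies is the one exposed.

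A reader might infer that every subject examined on Day 1 loses the ocular baseline. The documents do not support that: a same-day exam done before dosing is a valid baseline, and a post-dose exam with a missing time is kept by the date-only fallback. Nor are 30% or 50% expected losses. The range starts at zero, and no visible text says whether the eye-exam time is collected. SAP 8.9 to 8.11, which cover the three eye tests, are not visible in the public copy and may contain a specific convention.

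**Conclusion.** The Protocol contradicts itself on when the Day 1 eye tests and baseline biopsy are done relative to the first dose, and SAP 8.2.1 handles the resulting data inconsistently. The consequence is conditional. If a site follows the list on Day 1, the subject either has no ocular baseline (both times recorded) or has a post-dose one (either time missing). Only the first case removes the subject, and then from all three ocular endpoints at Weeks 4, 8 and 12. The number affected is unknown and is zero if sites follow footnote e. The 5%, 20% and 41% rises in standard error rest on assumed losses of 10%, 30% and 50%, even across arms. The primary endpoint is not touched. The point merits correction because the remedy is cheap and a missed baseline is permanent.

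**What to change.** **Protocol, order list in Section 5.1.** Add that on Day 1 the ophthalmologic assessments and the baseline biopsy are completed before step 5, or on an earlier day within the existing 5-day pre-dose window. Also reconcile Sections 4.5 and 5.4 with the list for Weeks 4 and 8. Dosing is scheduled at those visits too, so a Day 1 exception alone leaves the general rule and the list in conflict.

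**SAP 8.2.1.** State one rule for a Day 1 ocular exam done after the first dose, applied whether or not a clock time was recorded. Flag every such exam. If it is used as baseline, add a sensitivity analysis that excludes it; accepting it with no check would build in the post-dose baseline that the Protocol rules out.

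**Cost.** A sentence or two in each document. Sites that do the eye exam on the dosing day must schedule it before the first dose on Day 1.
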